9.5.2 Safety and tolerability data

The SAF Population will be used for all safety analyses. Safety analyses will be presented overall and by subgroup of subjects (e.g. cause of chronic pain), as appropriate.

9.5.2.1 Adverse events

Adverse events will be summarized according to the Medical Dictionary for Regulatory Activities (MedDRA) system organ class (SOC) and preferred term (PT). Any "higher-than-expected" event frequency will be investigated.

The number and percentage of subjects reporting each PT and SOC will be tabulated. A subject experiencing the same AE multiple times will only be counted once for the corresponding PT. Similarly, if a subject experiences multiple AEs within the same SOC, the individual will be counted only once for that SOC.

Similar tables will be presented for treatment-related AEs, Serious Adverse Events (SAEs), treatment related SAEs and AEs leading to discontinuation of study regimen. AEs that are reported as "possibly", "probably/likely" or "certainly" related to combination of study medication will be considered treatment related. AEs may also be summarized by highest severity and relationship to treatment. AEs will be listed for each subject.

Subject Death reported during the study will be summarized.

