Hospitalisation is usually defined as an overnight stay, i.e. admission prior to midnight and continuing into the following day. A visit to an out-patient facility or Emergency Department is not necessarily a hospitalisation, although the event leading to the visit could be an SAE. Hospitalisation for elective treatment of a pre-existing condition that did not worsen during the study is not considered a Serious Adverse Event unless a complication occurs during the hospitalisation.

Adverse Event Causality

The drug regimen -event relationship will be assessed using the following criteria:

Certain: A clinical event, including laboratory test abnormality occurring in a plausible time relationship to drug administration, and which cannot be explained by concurrent disease or other drugs or chemicals. The response to withdrawal of the drug (dechallenge) should be clinically

plausible. The event must be definitive pharmacologically or phenomenologically, using a satisfactory rechallenge procedure if necessary.

Probable /likely: A clinical event, including laboratory test abnormality, with a reasonable time sequence to administration of the drug, unlikely to be attributed to concurrent disease or other drugs or chemicals, and which follows a clinically reasonable response on withdrawal (dechallenge). Rechallenge information is not required to fulfil this definition.

Possible: A clinical event, including laboratory test abnormality, with a reasonable time sequence to administration of the drug, but which could also be explained by concurrent disease or other drugs or chemicals. Information on drug withdrawal may be lacking or unclear.

Unlikely: A clinical event, including laboratory test abnormality, with a temporal relationship to drug administration which makes a causal relationship improbable, and in which other drugs, chemicals or underlying disease provide plausible explanations.

Not assessable/unclassifiable: A report suggesting an adverse reaction, which cannot be judged because information is insufficient or contradictory, and which cannot be supplemented or verified.

Unrelated: A clinical event that is judged to be clearly and incontrovertibly due to extraneous causes (disease, environment, etc.) and meet the following criteria:

- The AE does not have a reasonable temporal relationship and can be explained by a commonly occurring alternative aetiology, or

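### Events that cannot be assessed for causality are left out of the treatment-related tables, so the related-event rates in the appended CANPAIN protocol are a lower bound

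*Protocol*

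**What the plan says.** All references are to the CANPAIN protocol in Appendix 1 unless stated otherwise.

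Section 7.1 assigns each adverse event to one of six causality classes: certain, probable/likely, possible, unlikely, not assessable/unclassifiable, and unrelated. The not-assessable class is "A report suggesting an adverse reaction, which cannot be judged because information is insufficient or contradictory, and which cannot be supplemented or verified".

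Section 9.5.2.1 then fixes which classes count. Events reported as possibly, probably/likely or certainly "related to combination of study medication will be considered treatment related". The list is closed, and not assessable is not on it.

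The rule feeds two of the planned tables: "Similar tables will be presented for treatment-related AEs, Serious Adverse Events (SAEs), treatment related SAEs and AEs leading to discontinuation of study regimen". A breakdown that would show the class separately is only optional: "AEs may also be summarized by highest severity and relationship to treatment". Every event still reaches the listings: "AEs will be listed for each subject".

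**The concern.** Two of the three excluded classes are excluded because someone judged causality to be improbable or absent. The third is excluded because nobody could judge. Grouping them treats missing or contradictory information as if it were evidence against a causal link, although the class is defined as a report that suggests a reaction.

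Safety and tolerability are a stated aim (section 5). The study is single arm, and section 6.2 says that tolerability data are not required from the matched cohort. With no comparator for harms, the causality class is one of the few means of attributing events to the product. A related-event rate that leaves out suspected but unjudged reactions would look better the less is known about them, and readers would not see that it is a lower bound.

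**Working it through.** **Step 1: the classes side by side (sections 7.1 and 9.5.2.1).**

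| Class | Basis in section 7.1 | Counted as related in 9.5.2.1 |
|---|---|---|
| Certain | Positive judgement for causality | Yes |
| Probable/likely | Positive judgement for causality | Yes |
| Possible | Another cause could explain it; "Information on drug withdrawal may be lacking or unclear" | Yes |
| Unlikely | "temporal relationship to drug administration which makes a causal relationship improbable" | No |
| Unrelated | "clearly and incontrovertibly due to extraneous causes" | No |
| Not assessable/unclassifiable | Suggests a reaction; no judgement either way | No |

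The possible class is counted even with gaps in the information. Unlikely and unrelated are left out on a judgement against causality. Not assessable is the only class left out without such a judgement.

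**Step 2: direction.** Take the safety set of section 9.3 (everyone with at least one dose) as denominator, and take the classification of all other events as given. Let

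- r = share of subjects with a counted related event in a given table line;
- u = share with a not-assessable event and no counted related event in that line (section 9.5.2.1 counts a subject once per preferred term and once per system organ class, so other subjects add nothing);
- f = fraction of the u subjects whose event was in truth caused by the product, between 0 and 1.

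Rate under the rule: r. Rate including the truly related part: r + f·u. Shortfall: f·u, which is never negative and is at most u. Relative shortfall: f·u / (r + f·u).

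The rule therefore gives the lower bound r. Counting the whole class gives the upper bound r + u.

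**Step 3: size.** The protocol states no value for r, u or f, so there is no figure to reproduce and no estimate to give. The table below only shows how the formula behaves, with assumed values r = 20% and u = 1% or 10% and the planned 5000 participants (1000 related subjects under the rule).

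| u (assumed) | f (assumed) | Rate r + f·u | Subjects | Relative shortfall |
|---|---|---|---|---|
| 1% or 10% | 0 | 20% | 1000 | 0 |
| 1% | 0.5 | 20.5% | 1025 | 0.5/20.5 = 2.4% |
| 1% | 1 | 21% | 1050 | 1/21 = 4.8% |
| 10% | 0.5 | 25% | 1250 | 5/25 = 20% |
| 10% | 1 | 30% | 1500 | 10/30 = 33.3% |

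The result depends almost entirely on values the documents do not give, and it includes zero.

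**Step 4: what is not affected.** The tables of all AEs, all SAEs and AEs leading to discontinuation, the summary of deaths and the listings in section 9.5.2.1 do not depend on the causality class. A not-assessable event appears in all those that apply to it.

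**The case against.** The strongest reply is that section 9.5.2.1 only defines one table category. It does not call a not-assessable event unrelated, and section 7.1 does not say that the class must count as related. Counting all such events, including those with contradictory information, would replace a lower bound with an upper bound, and which of the two leads is partly convention. This stands as far as it goes. It is the reason for asking that both bounds be readable; it does not justify a plan in which only the lower one is sure to appear.

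Three stronger readings are tempting, and the documents do not support them.

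- A reader might infer that the related rates will be materially too low. No frequency is given, and there is no shortfall if no such event is caused by the product.
- A reader might infer that the related tables alone carry the safety conclusion. Section 9.5.2.1 puts the all-causality tabulation first and says that unexpectedly frequent events will be investigated, without a causality filter. Section 6.6.1 adds daily tolerability scores.
- A reader might infer that unjudgeable events will be common because reporting is remote and follow-up weak. Section 7.2 has AEs elicited at each visit and followed until resolved, section 6.4.5 requires efforts to contact those who miss visits, section 6.4.8 continues follow-up after treatment stops, and section 6.7.2.1 obtains laboratory reports at the start and quarterly. The class is also narrow: the information must be impossible to supplement or verify.

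The reach is limited too. The feasibility study's own safety objective (section 3.1 of the main document) counts patients with safety issues and uses no causality class. The point concerns the appended protocol, which is marked as a draft and is intended for resubmission.

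**Conclusion.** The point holds in a limited form. The related-AE and related-SAE tables, produced as written, omit events that the protocol itself describes as suggesting a reaction. They place those events with events judged not to be caused by the product. The resulting rates are a lower bound with respect to this class: they can be too low because of the rule, never too high. The gap is at most the share of subjects whose only candidate event in that table line is not assessable. The documents do not allow it to be estimated, and it may be nil.

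This is not merely a detail left to the statistical analysis plan, because the protocol fixes the list of counted classes. The only table that would show the omitted class is optional. The conclusion assumes that the six classes are applied as defined and takes the classification of the other events as given. It does not mean that events are lost or that the overall safety tables are wrong.

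**What to change.** In section 9.5.2.1, state that events classed not assessable/unclassifiable count as treatment related in the related-AE and related-SAE tables. Always add a separate row giving the number of subjects who are included only because of a not-assessable event. The table total is then the inclusive rate (upper bound), and the total minus that row is the assessable-only rate (lower bound). The row must count subjects, not events, and must leave out those who already have a counted related event; otherwise the subtraction fails.

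The cost is one sentence and one table row. No new data are needed and patient care does not change. The downside is a slightly less favourable related-event rate that may include some events the product did not cause, which the separate row makes visible. As CANPAIN is to be resubmitted, the text can be changed beforehand.

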9.5.2.2 Other Safety Data

Drug Regimen exposure and standard of care analgesic therapy will be summarized.

9.6 Measures to reduce bias

See Section 7.2.

10. ETHICS AND REGULATIONS

10.1 Research ethics committees and competent authority

The clinical trial authorisation granted by MHRA and a favourable opinion from the relevant research ethics committee (REC) will be obtained prior to the start of the study. The local authorities will be notified about the study as required by law.

The MHRA and the REC will be notified about the end of the trial and a report summarising the study results will be sent to the MHRA and the REC within one year after the end of the trial. If the trial is terminated early, the MHRA and the REC will be notified within 15 days.

10.2 Ethical conduct of the study

The study will be conducted in accordance with the ethical principles set forth in the Declaration of Helsinki (including amendments). A copy of the declaration is included in Appendix 1 of this protocol.

10.3 Participant information and consent

Written informed consent will be obtained from all participants prior to entry into the study. The investigator will explain to each participant orally and in writing, the nature, significance, risks and implications of the trial before inclusion. In particular, the participants will be informed about the following:

- the possibility of withdrawing from the clinical trial at any time by revoking the consent and without any resulting disadvantage.
- how personal and health-related data will be collected and used during the study.

All participants will receive a copy of their signed and dated informed consent form.

10.4 Legal and regulatory requirements

This trial will be carried out in accordance with

- Good Clinical Practice (GCP) as required by EU Directive 2001/20/EC, the relevant laws and regulations of the country in which the study takes place.
- Standard operating procedures (SOPs for clinical investigation and documentation).

11. STUDY ADMINISTRATION

11.1 Responsibilities

Harley Street (CPC) Limited is the sponsor of this study and will organise the performance of this study. The representative for the sponsor is [name].

11.2 Protocol changes

Amendments to this study protocol may be made following the procedures specified by local laws and regulations. Substantial amendments to this study protocol may be implemented only if the approval of the MHRA and/or a favourable opinion of the REC have been obtained.

Substantial amendments to the conduct of the clinical trial may arise from changes to the protocol or from new information relating to the scientific documents in support of the trial. Amendments to the trial are regarded as “substantial” where they are likely to have a significant impact on:

- the safety, physical health and mental integrity of the participants;
- the scientific value of the trial; or
- the conduct or management of the trial.

If a new event occurs related to the conduct of the trial which may affect the safety of the participants, the sponsor and the investigator will take appropriate safety measures to protect the participants against any immediate hazard. The sponsor will immediately inform the MHRA and REC of the new events and the measures taken.

11.3 Publication of results

The original CRFs and the data otherwise obtained during the study under this study protocol will become the property of the sponsor.

Information about this trial and the results will be posted according to applicable national or regional regulations and laws.

11.4 Clinical study report

After completion of the study, the results will be tabulated, evaluated and issued as a complete final clinical study report according to the ICH-E3 Note for guidance on structure and content of clinical study reports.

The sponsor will send a summary of this clinical study report to the REC and MHRA within one year after the end of the trial (after the last participant’s treatment).

11.5 Retention of study records

Records and documents pertaining to the conduct of the study and the distribution of the treatment drug (e.g. ICFs, laboratory slips, medication inventory records, and other pertinent information) must be retained by the Investigator for a period of at least 10 years.

CRF data will be kept for a period of at least 15 years.

General Principles

3. The Declaration of Geneva of the WMA binds the physician with the words, "The health of my patient will be my first consideration," and the International Code of Medical Ethics declares that, "A physician shall act in the patient's best interest when providing medical care."

4. It is the duty of the physician to promote and safeguard the health, well-being and rights of patients, including those who are involved in medical research. The physician's knowledge and conscience are dedicated to the fulfilment of this duty.

5. Medical progress is based on research that ultimately must include studies involving human subjects.

6. The primary purpose of medical research involving human subjects is to understand the causes, development and effects of diseases and improve preventive, diagnostic and therapeutic interventions (methods, procedures and treatments). Even the best proven interventions must be evaluated continually through research for their safety, effectiveness, efficiency, accessibility and quality.

7. Medical research is subject to ethical standards that promote and ensure respect for all human subjects and protect their health and rights.

8. While the primary purpose of medical research is to generate new knowledge, this goal can never take precedence over the rights and interests of individual research subjects.

9. It is the duty of physicians who are involved in medical research to protect the life, health, dignity, integrity, right to self-determination, privacy, and confidentiality of personal information of research subjects. The responsibility for the protection of research subjects must always rest with the physician or other health care professionals and never with the research subjects, even though they have given consent.

10. Physicians must consider the ethical, legal and regulatory norms and standards for research involving human subjects in their own countries as well as applicable international norms and standards. No national or international ethical, legal or regulatory requirement should reduce or eliminate any of the protections for research subjects set forth in this Declaration.

11. Medical research should be conducted in a manner that minimises possible harm to the environment.

12. Medical research involving human subjects must be conducted only by individuals with the appropriate ethics and scientific education, training and qualifications. Research on patients or healthy volunteers requires the supervision of a competent and appropriately qualified physician or other health care professional.

13. Groups that are underrepresented in medical research should be provided appropriate access to participation in research.

14. Physicians who combine medical research with medical care should involve their patients in research only to the extent that this is justified by its potential preventive, diagnostic or therapeutic value and if the physician has good reason to believe that participation in the research study will not adversely affect the health of the patients who serve as research subjects.

15. Appropriate compensation and treatment for subjects who are harmed as a result of participating in research must be ensured.

Risks, Burdens and Benefits

16. In medical practice and in medical research, most interventions involve risks and burdens.

Medical research involving human subjects may only be conducted if the importance of the objective outweighs the risks and burdens to the research subjects.

17. All medical research involving human subjects must be preceded by careful assessment of predictable risks and burdens to the individuals and groups involved in the research in comparison with foreseeable benefits to them and to other individuals or groups affected by the condition under investigation.

Measures to minimise the risks must be implemented. The risks must be continuously monitored, assessed and documented by the researcher.

18. Physicians may not be involved in a research study involving human subjects unless they are confident that the risks have been adequately assessed and can be satisfactorily managed.

When the risks are found to outweigh the potential benefits or when there is conclusive proof of definitive outcomes, physicians must assess whether to continue, modify or immediately stop the study.

Vulnerable Groups and Individuals

19. Some groups and individuals are particularly vulnerable and may have an increased likelihood of being wronged or of incurring additional harm.

All vulnerable groups and individuals should receive specifically considered protection.

20. Medical research with a vulnerable group is only justified if the research is responsive to the health needs or priorities of this group and the research cannot be carried out in a non-vulnerable group. In addition, this group should stand to benefit from the knowledge, practices or interventions that result from the research.

Scientific Requirements and Research Protocols

21. Medical research involving human subjects must conform to generally accepted scientific principles, be based on a thorough knowledge of the scientific literature, other relevant sources of information, and adequate laboratory and, as appropriate, animal experimentation. The welfare of animals used for research must be respected.

22. The design and performance of each research study involving human subjects must be clearly described and justified in a research protocol.

The protocol should contain a statement of the ethical considerations involved and should indicate how the principles in this Declaration have been addressed. The protocol should include information regarding funding, sponsors, institutional affiliations, potential conflicts of interest, incentives for subjects and information regarding provisions for treating and/or compensating subjects who are harmed as a consequence of participation in the research study.

In clinical trials, the protocol must also describe appropriate arrangements for post-trial provisions.

Research Ethics Committees

23. The research protocol must be submitted for consideration, comment, guidance and approval to the concerned research ethics committee before the study begins. This committee must be transparent in its functioning, must be independent of the researcher, the sponsor and any other undue influence and must be duly qualified. It must take into consideration the laws and regulations of the country or countries in which the research is to be performed as well as applicable international norms and standards but these must not be allowed to reduce or eliminate any of the protections for research subjects set forth in this Declaration.

The committee must have the right to monitor ongoing studies. The researcher must provide monitoring information to the committee, especially information about any serious adverse events. No amendment to the protocol may be made without consideration and approval by the committee. After the end of the study, the researchers must submit a final report to the committee containing a summary of the study's findings and conclusions.

Privacy and Confidentiality

24. Every precaution must be taken to protect the privacy of research subjects and the confidentiality of their personal information.

Informed Consent

25. Participation by individuals capable of giving informed consent as subjects in medical research must be voluntary. Although it may be appropriate to consult family members or community leaders, no individual capable of giving informed consent may be enrolled in a research study unless he or she freely agrees.

26. In medical research involving human subjects capable of giving informed consent, each potential subject must be adequately informed of the aims, methods, sources of funding, any possible conflicts of interest, institutional affiliations of the researcher, the anticipated benefits and potential risks of the study

and the discomfort it may entail, post-study provisions and any other relevant aspects of the study. The potential subject must be informed of the right to refuse to participate in the study or to withdraw consent to participate at any time without reprisal. Special attention should be given to the specific information needs of individual potential subjects as well as to the methods used to deliver the information.

After ensuring that the potential subject has understood the information, the physician or another appropriately qualified individual must then seek the potential subject's freely-given informed consent, preferably in writing. If the consent cannot be expressed in writing, the non-written consent must be formally documented and witnessed.

All medical research subjects should be given the option of being informed about the general outcome and results of the study.

27. When seeking informed consent for participation in a research study the physician must be particularly cautious if the potential subject is in a dependent relationship with the physician or may consent under duress. In such situations the informed consent must be sought by an appropriately qualified individual who is completely independent of this relationship.

28. For a potential research subject who is incapable of giving informed consent, the physician must seek informed consent from the legally authorised representative. These individuals must not be included in a research study that has no likelihood of benefit for them unless it is intended to promote the health of the group represented by the potential subject, the research cannot instead be performed with persons capable of providing informed consent, and the research entails only minimal risk and minimal burden.

29. When a potential research subject who is deemed incapable of giving informed consent is able to give assent to decisions about participation in research, the physician must seek that assent in addition to the consent of the legally authorised representative. The potential subject's dissent should be respected.

30. Research involving subjects who are physically or mentally incapable of giving consent, for example, unconscious patients, may be done only if the physical or mental condition that prevents giving informed consent is a necessary characteristic of the research group. In such circumstances the physician must seek informed consent from the legally authorised representative. If no such representative is available and if the research cannot be delayed, the study may proceed without informed consent provided that the specific reasons for involving subjects with a condition that renders them unable to give informed consent have been stated in the research protocol and the study has been approved by a research ethics committee. Consent to remain in the research must be obtained as soon as possible from the subject or a legally authorised representative.

31. The physician must fully inform the patient which aspects of their care are related to the research. The refusal of a patient to participate in a study or the patient's decision to withdraw from the study must never adversely affect the patient-physician relationship.

32. For medical research using identifiable human material or data, such as research on material or data contained in biobanks or similar repositories, physicians must seek informed consent for its collection, storage and/or reuse. There may be exceptional situations where consent would be impossible or impracticable to obtain for such research. In such situations the research may be done only after consideration and approval of a research ethics committee.

Use of Placebo

33. The benefits, risks, burdens and effectiveness of a new intervention must be tested against those of the best proven intervention(s), except in the following circumstances:

Where no proven intervention exists, the use of placebo, or no intervention, is acceptable; or

Where for compelling and scientifically sound methodological reasons the use of any intervention less effective than the best proven one, the use of placebo, or no intervention is necessary to determine the efficacy or safety of an intervention

and the patients who receive any intervention less effective than the best proven one, placebo, or no intervention will not be subject to additional risks of serious or irreversible harm as a result of not receiving the best proven intervention.

Extreme care must be taken to avoid abuse of this option.

Post-Trial Provisions

34. In advance of a clinical trial, sponsors, researchers and host country governments should make provisions for post-trial access for all participants who still need an intervention identified as beneficial in the trial. This information must also be disclosed to participants during the informed consent process.

Research Registration and Publication and Dissemination of Results

35. Every research study involving human subjects must be registered in a publicly accessible database before recruitment of the first subject.

36. Researchers, authors, sponsors, editors and publishers all have ethical obligations with regard to the publication and dissemination of the results of research. Researchers have a duty to make publicly available the results of their research on human subjects and are accountable for the completeness and accuracy of their reports. All parties should adhere to accepted guidelines for ethical reporting. Negative and inconclusive as well as positive results must be published or otherwise made publicly available. Sources of funding, institutional affiliations and conflicts of interest must be declared in the publication. Reports of research not in accordance with the principles of this Declaration should not be accepted for publication.

Unproven Interventions in Clinical Practice

37. In the treatment of an individual patient, where proven interventions do not exist or other known interventions have been ineffective, the physician, after seeking expert advice, with informed consent from the patient or a legally authorised representative, may use an unproven intervention if in the physician's judgement it offers hope of saving life, re-establishing health or alleviating suffering. This intervention should subsequently be made the object of research, designed to evaluate its safety and efficacy. In all cases, new information must be recorded and, where appropriate, made publicly available.

C. ADDITIONAL PRINCIPLES FOR MEDICAL RESEARCH COMBINED WITH MEDICAL CARE

31. The physician may combine medical research with medical care only to the extent that the research is justified by its potential preventive, diagnostic or therapeutic value and if the physician has good reason to believe that participation in the research study will not adversely affect the health of the patients who serve as research participants.
32. The benefits, risks, burdens and effectiveness of a new intervention must be tested against those of the best current proven intervention, except in the following circumstances:
 - The use of placebo, or no treatment, is acceptable in studies where no current proven intervention exists; or
 - Where for compelling and scientifically sound methodological reasons the use of placebo is necessary to determine the efficacy or safety of an intervention and the patients who receive placebo or no treatment will not be subject to any risk of serious or irreversible harm. Extreme care must be taken to avoid abuse of this option.
